16.9 Columbia Suicide Severity Rating Scale (C-SSRS)

The C-SSRS measures both suicidal ideation and suicidal behavior and will be completed on Day 1 (before the first injection of study drug), at each subsequent study visit, or, if applicable, at discontinuation from the study. The Baseline version of the C-SSRS (Appendix J) will be used to assess lifetime suicidality on Day 1. At all other protocol-specified time points, the C-SSRS – Since Last Visit version (Appendix K) will be used to assess the subject's suicidality since the last assessment.

The C-SSRS has three subscales: suicidal ideation, suicidal behavior, and intensity of suicidal ideation. Both suicidal ideation subscale and suicidal behavior subscale have 5 yes-no items each, with a sum score ranging from 0 to 5 and higher score indicating greater severity. The intensity of suicidal ideation has 5 items, with a sum score ranging from 2 to 25 and higher score indicating greater risk.

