2.6.2 Safety measures

Adverse events are recorded at each study visit, starting from the first injection of MYOBLOC on Day 1 of Treatment Session 1 and ending at study completion (i.e., 52 ± 1 week). Subjects who discontinue because of an adverse event before study completion will be contacted 13 weeks (±3 days) after their last injection of study drug to assess the adverse event. Serious adverse events, adverse events of special interest, and other immediately reportable adverse events were collected during the study period (or within 13 weeks ±3 days of last study drug injection for subjects discontinuing participation prematurely). Dental and oral health are followed closely throughout the course of the study by monitoring dental adverse events (DAE), as defined in the study protocol.

Vital signs (blood pressure, pulse, respiratory rate, and temperature) are measured after sitting quietly for at least 5 minutes at screening and each study visit, if applicable, at early termination from the study.

Subjects' suicidal ideation and behavior are measured at each study visit (including Day 1 and Weeks 4, 8, 13, 17, 26, 30, 39, 43, and 52) or, if applicable, early termination from the study, using the Columbia Suicidal Severity Rating Scale (C-SSRS). The C-SSRS baseline version (Appendix I of the protocol) will be used for Day 1, whereas the C-SSRS since last visit version (Appendix J of the protocol) will be used for all of the other visits. The C-SSRS has three subscales: suicidal ideation (Categories 1-5), suicidal behavior (Categories 6-10), and intensity of suicidal ideation. Both suicidal ideation subscale and suicidal behavior subscale have 5 yes-no categories each, with a sum score ranging from 0 to 5 and higher score indicating greater severity.

Category 1 – Wish to be Dead

Category 2 – Non-specific Active Suicidal Thoughts

Category 3 – Active Suicidal Ideation with Any Methods (Not Plan) without Intent to Act

Category 4 – Active Suicidal Ideation with Some Intent to Act, without Specific Plan

Category 5 – Active Suicidal Ideation with Specific Plan and Intent

- Category 6 – Actual Attempt
- Category 7 – Interrupted Attempt
- Category 8 – Aborted Attempt
- Category 9 – Preparatory Acts or Behavior
- Category 10 – Suicidal Behavior

The intensity of suicidal ideation has 5 items (2 are scored from 1 through 5 and the other three from 0 to 5), with a sum score ranging from 2 to 25 where higher score indicate greater risk.

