For the analysis, an intensity of suicidal ideation will be defined as the maximum suicidal ideation category (1-5 on the C-SSRS) present at the assessment. A score of 0 will be assigned if no ideation is present.

Clinical laboratory tests are conducted at screening, Weeks 13, 26, as needed at the Investigator's discretion throughout the study and at study completion (i.e., Week 52) or, if applicable, at early termination from the study. Laboratory tests are analyzed by a central laboratory and include the following parameters:

Serum Chemistry:
cholesterol, phosphorus, sodium (Na ⁺), potassium (K ⁺), calcium (Ca), urea nitrogen (BUN), creatinine, albumin, total protein, aspartate transaminase (AST), alanine transaminase (ALT), alkaline phosphatase (ALP), gamma-glutamyl transferase (GGT), uric acid, total bilirubin, glucose, and lactate dehydrogenase (LDH).
Hematology:
hemoglobin, hematocrit, platelet count, red blood cell (RBC) count, MCV, MCH, MCHC, white blood cell (WBC) count, WBC differentials (%), including bands, neutrophils, lymphocytes, monocytes, eosinophils, and basophils
Urinalysis:
specific gravity, pH, glucose, blood, protein, color, nitrites, ketones, bilirubin, urobilinogen, and leukocyte esterase.

A complete physical examination is performed at screening, Weeks 4, 13, 26, 39, and at study completion (i.e., Week 52) or, if applicable, at early termination from the study. The complete examination will involve gross examination of general appearance; head, ears, eyes, nose and throat; skin; extremities; chest; abdomen; and lymph nodes. Cardiac and pulmonary auscultation and measurement of vital signs and weight will also be conducted as part of the complete physical exam. A brief physical examination, consisting of cardiac and pulmonary auscultation is performed on Day 1 prior to injection of study drug and at Weeks 8, 17, 30, and 43. Height will be recorded at screening only. Lung functioning is measured for subjects with ALS, using forced vital capacity (liter) (FVC), and in other subjects if warranted, at the discretion of the Investigator at screening, before the first injection of study drug on Day 1, at Weeks 4, 8 (as clinically warranted), and 13. Thereafter, FVC will be checked if warranted at Investigators' discretion (such as if the subject has ALS). If any of the Physical Exam findings were abnormal and clinically

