Withdrawals due to adverse events will be summarized for each body system and preferred term. Serious adverse events (SAEs) (including deaths) will be listed for individual events.

Narratives will be provided for all deaths, non-fatal serious adverse events, and subjects withdrawn due to adverse events.

Vital Signs and Weight

Vital signs and weight will be summarized descriptively by treatment session at pre-injection (i.e., Day 1 and Weeks 13, 26, and 39) and at each post-injection time point of 4 weeks post-injection (i.e., Weeks 4, 17, 30, and 43), 8 weeks post-injection (i.e., Week 8 first treatment session only), and 13 weeks post-injection (i.e., Weeks 13, 26, 39, and 52). The change scores in vital signs and weight from baseline at 4 weeks, 8 weeks (first treatment session only), and 13 weeks post-injection will be summarized descriptively.

Neurologic Exam

Abnormal findings of neurological exam data will be listed, respectively, for individual subjects.

Lung Functioning Test

Findings of forced vital capacity (FVC) data will be listed, respectively, for individual subjects.

Physical Examination

A complete Physical Examination was performed at Screening, Week 4, Week 13, Week 26, Week 39, Week 52, and Early Discontinuation. A brief Physical Examination was performed at Day 1, Week 8, Week 17, Week 30, and Week 43 when body weight, height and body mass index (BMI) were recorded. If any of the Physical Examination findings were abnormal and clinically significant prior to treatment, the event was recorded as medical history, while if occurred after treatment the event was recorded as a TEAE.

Suicidality Assessment

For each treatment session, each of the three C-SSRS subscales (suicidal ideation, suicidal behavior, and intensity of suicidal ideation) will be summarized descriptively for continuous variable at each pre-injection visit (i.e., Day 1 and Weeks 13, 26, and 39) and at each post-injection time point of 4 weeks post-injection (i.e., Weeks 4, 17, 30, and 43), 8 weeks post-injection (i.e., Week 8, first treatment session only), and 13 weeks post-injection (i.e., Weeks 13, 26, 39, and 52). The change scores in C-SSRS subscales from pre-injection at 4 weeks, 8 weeks (first treatment session only), and 13 weeks post-injection will be summarized descriptively.

Dental Examination and Oral Examination

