5.12 Suicidality Assessment

For the safety population, descriptive and inferential statistics of C-SSRS will be presented at pre-injection and post-injection time points, for each of the three C-SSRS subscales (suicidal ideation, suicidal behavior, and intensity of suicidal ideation) for Treatment Session 1, Treatment Session 2, Treatment Session 3, and for Treatment Session 4. The change scores in C-SSRS subscales from pre-injection at 4 weeks, 8 weeks (first Treatment Session only), and 13 weeks post-injection were summarized descriptively.

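### The C-SSRS behavior score counts 'yes' answers and so does not rank severity, and the plan commits to no number of subjects with suicidal ideation or behavior

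*SAP*

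**What the plan says.** **Scoring.** SAP 2.6.2: "Both suicidal ideation subscale and suicidal behavior subscale have 5 yes-no categories each, with a sum score ranging from 0 to 5". Protocol 16.9 has the same rule: "Both suicidal ideation subscale and suicidal behavior subscale have 5 yes-no items each, with a sum score ranging from 0 to 5". In both documents the full clause on the score reads "with a sum score ranging from 0 to 5 and higher score indicating greater severity", and neither gives weights. The SAP's behavior list starts with "Category 6 – Actual Attempt", passes through interrupted and aborted attempts to "Category 9 – Preparatory Acts or Behavior", and ends with a general suicidal behavior item, Category 10.

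**Third subscale.** SAP 2.6.2 first describes intensity as a five-item sum from 2 to 25. For the analysis it substitutes another quantity: "an intensity of suicidal ideation will be defined as the maximum suicidal ideation category (1-5 on the C-SSRS) present at the assessment", with 0 if there is none. Behavior has no corresponding rule.

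**Analysis.** Under SAP 2.9.2, "each of the three C-SSRS subscales (suicidal ideation, suicidal behavior, and intensity of suicidal ideation) will be summarized descriptively for continuous variable", by visit and session, with descriptive change scores. SAP 2.9 defines a continuous summary as n, mean, SD, minimum, median and maximum. SAP 5.12 goes further: "descriptive and inferential statistics of C-SSRS will be presented at pre-injection and post-injection time points". It names no test. Protocol 17.7 names a paired t-test on the change scores, by dose group.

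**Listings.** SAP 2.8 and protocol 17.6 promise that all records will be listed. Neither SAP 2.9.2 nor SAP 5.12 names a C-SSRS listing, a shift table, or a count of subjects with ideation or behavior.

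**The concern.** The C-SSRS is a named safety endpoint (protocol 9.1). Its clinical question is whether any subject had suicidal ideation or behavior after injection, in how many subjects, and of what kind. The behavior categories are different kinds of event, so adding one point for each 'yes' need not order subjects by severity, although both documents say it does. Averaging that sum over a population in which nearly everyone scores 0 shrinks a rare, serious event to a figure in the third decimal.

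Elsewhere the plan reports safety in the natural unit. Adverse events, events of special interest, dental events and toxin-spread events get numbers and proportions of subjects (SAP 2.9.2 and 5.3 to 5.6), and laboratory tests get shift tables (SAP 5.11). At stake is a readable answer on suicidality, and a non-significant test on a mean being read as reassurance.

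**Working it through.** **Inputs.** Five yes/no categories per subscale, summed without weights (SAP 2.6.2, protocol 16.9). 187 subjects, within a planned range of 120 to 200 (SAP 2.5). Two-sided testing is assumed at the 5% level of SAP 2.9. Per-session n is not stated, so n = 100 is assumed as a reduced figure for later sessions.

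**The plan's own figures.** Five 0/1 items sum to between 0 and 5, as stated. The intensity range also reproduces: two items scored 1 to 5 and three scored 0 to 5 give a minimum of 2 × 1 = 2 and a maximum of 5 × 5 = 25.

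**Does the sum rank severity?**

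| Endorsed | Sum | Maximum category |
|---|---|---|
| Behavior: actual attempt {6} | 1 | not planned |
| Behavior: preparatory act {9} | 1 | not planned |
| Behavior: aborted attempt and preparatory act {8, 9} | 2 | not planned |
| Ideation: plan and intent {5} | 1 | 5 |
| Ideation: the two mildest {1, 2} | 2 | 2 |

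For behavior, an attempt ties with a preparatory act and falls below the pair {8, 9}. For ideation the sum is misordered in the same way, but the maximum-category score puts {5} above {1, 2}.

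The result does not depend on Category 10. If it were ticked alongside every behavior, each behavior row would rise by 1 (2, 2 and 3), with the same tie and the same reversal.

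**What the continuous summary shows.** Let k of n subjects score 1 and the rest 0.

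- Mean = k/n. For k = 1: 1/187 = 0.0053 (1/120 = 0.0083; 1/200 = 0.0050).
- SD = √[k(n − k) / (n(n − 1))]. For k = 1 this is 1/√n = 1/√187 = 0.073.
- Median 0, maximum 1.

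**What a t-test on change shows**, if the k subjects each move from 0 to 1 and nobody else changes: t = √[k(n − 1)/(n − k)].

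| New cases, n = 187 | t | p |
|---|---|---|
| 1 | √(1 × 186/186) = 1.00 | 0.32 |
| 2 | √(2 × 186/185) = 1.42 | 0.16 |
| 3 | √(3 × 186/184) = 1.74 | 0.083 |
| 4 | √(4 × 186/183) = 2.02 | 0.045 |

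For one case t is exactly 1 at any n. The threshold of four cases is the same at n = 100, 120 and 200.

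**What a count would show.** One case in 187 is 0.53% (exact 95% CI 0.01% to 2.94%). In 120 it is 0.83% (0.02% to 4.56%), and in 200 it is 0.50% (0.01% to 2.75%). No cases in 187 gives 0% with an upper limit of 1.95%, which a mean of 0 cannot supply.

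**The case against.** Several stronger readings are tempting, and the documents do not support them.

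- **That only means are reported.** The summary also gives SD, minimum, median and maximum. With no cases SD and maximum are both 0; with one case the maximum is 1. A single case is therefore visible in the row. What the row does not show is the kind of behavior or the number of subjects.
- **That a case would be lost from the report.** All records are to be listed, and an attempt that met the adverse event or SAE definitions would be tabulated and listed; an SAE would also have a narrative. This stands. But a full record listing is not a summary of an endpoint, and adverse event capture is a separate route that need not pick up every positive C-SSRS answer.
- **That ideation severity is lost.** The maximum ideation category is analysed, so the misordered ideation sum does limited harm.
- **That one event is counted twice through Category 10.** The C-SSRS forms are not in the available text, so this cannot be checked.
- **That no C-SSRS count or listing exists anywhere.** The SAP's lists of table and listing shells (Sections 7 and 8) are not in the available text. The point is limited to what SAP 2.9.2 and 5.12 commit to.

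There is also a fair defence of the means: the protocol prespecifies both the scoring and the paired t-test, so the SAP is following it. That argues for keeping those summaries as supplementary and documenting any change. It does not make the behavior sum a severity score.

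**Conclusion.** The concern holds, mainly for behavior. The stated property that a higher score means greater severity is false for the behavior sum by direct scoring from the SAP's own list. The planned table gives neither the number of subjects with an event nor its kind. At 187 subjects, one case moves the mean by 0.0053 on a 0 to 5 scale, and one to three new cases give a non-significant t-test.

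These figures assume one point per case, nobody else changing, and the full sample. Smaller later sessions raise the mean (0.0100 at the assumed n = 100) but leave the pattern of p-values almost unchanged. The defect is one of reporting for a named safety endpoint. It does not invalidate the trial or its data, and it should be corrected before the tables are produced.

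**What to change.** In SAP 2.9.2 and 5.12, make the main C-SSRS summary the number (%) of subjects, per session and over the study, with:

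1. any ideation, and ideation by highest category reached (1 to 5);
2. any behavior, and each behavior category (6 to 10) counted separately. Highest category number must not be used here: the numbering runs from actual attempt (6) to preparatory acts (9) and a general item (10), so a subject with {6, 9} would be filed under the preparatory act;
3. post-injection ideation or behavior, split by whether any was recorded on the Day 1 form. That form covers lifetime (protocol 16.9), so a rule of being worse than before the first injection would miss a repeat event in a subject with a lifetime history.

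List each positive case by subject, visit and category. Drop the inferential tests on the ideation and behavior sums, or keep the protocol's continuous summaries as supplementary only. Reconcile SAP 2.9.2 (descriptive only) with SAP 5.12 (descriptive and inferential), and record the departure from protocol 17.7.

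Cost: one added table and listing from data already collected, and a documented departure from the protocol. Trial conduct does not change.

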2.6.3 Other measures

Prior treatment for sialorrhea and concomitant medications (including those taken within 30 days before screening) taken over the course of the study will be recorded.

The medical history with disease history, co-morbidities, relevant past illness, and surgical procedures performed within the prior 6 months are recorded at screening. Subjects are also evaluated for presence or prior history of aspiration, aspiration pneumonia, choking, and/or dysphagia.

2.7 Drug Concentration and PK Measurements

No drug concentration measures will be taken in this trial.

2.8 Handling of Missing, Incomplete, and Repeat Data

Missing Data of Effectiveness Measures

Missing post-injection measurements will not be imputed, whereas missing measurements at the pre-injection of each treatment session will be imputed by the site-specific average of those subjects who receive the treatment at the corresponding treatment session.

Missing Data of Safety Parameters

For safety parameters, missing or invalid data will be treated as missing for the corresponding assessment, except that for partial start dates of adverse events, missing day and month will be imputed to the date of first injection. Completely unknown start dates will be imputed to date of first injection. If day is missing and month and year are present then day is either set to the 1st of the month or the day of the month for the first injection.

Handling of Repeated Data Records

All data records with valid data of efficacy and safety measures are identified for initial and repeat within each study visit and/or assessment time point. Should repeated data records exist within a study visit and/or assessment time point, the initial data record will be utilized for any statistical analyses of the corresponding study visit and/or assessment time point. All existing data records including the repeat data records in the study database will be presented in data listings and CRF data tabulations.

Any resultant incomplete or missing data of either efficacy or safety parameters will be treated as missing in the statistical analyses involving these parameters.

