17.9 Statistical Methods for Effectiveness

As subjects will receive multiple single-dose injections, each single-dose injection plus its follow-up period will be considered as a treatment session. Post-injection effectiveness endpoints over each of the treatment sessions include USFR, CGI-C, CGI-S, DFSS-I, PGI-C, PGI-S, DIS, and DFSS-S at the injection visit (i.e., Day 1, Weeks 13, 26, and 39), 4 weeks post-injection (i.e., Weeks 4, 17, 30, and 43), 8 weeks post-injection (i.e., Week 8, first Treatment Session only), and 13 weeks post-injection (i.e., Weeks 13, 26, 39, and 52). The pre-injection time points are Day 1 and Weeks 13, 26, and 39 for each of the consecutive treatment sessions. Missing post-injection measurements will not be imputed, whereas missing measurements at the pre-injection of each treatment session will be imputed by the site-specific average of those subjects who receive the treatment at the corresponding treatment session.

For each treatment session, effectiveness analysis of the treatment response will be performed on USFR change from pre-injection, CGI-C, CGI-S, PGI-C, PGI-S, and DIS change from pre-injection, DFSS-I change from pre-injection, and DFSS-S change from

pre-injection at each of the post-injection time points for the ITT population, using a paired t-test. The ITT population will be grouped into three groups by the actual doses the subject received at each session as the following: low dose (2,500 to 2,999 Units), medium dose (3,000 to 3,499 Units), and high dose (3,500 Units).

In addition, the proportion of treatment responders will be reported for the CGI-C and PGI-C at both pre-injection and post-injection time points over each treatment session. Before the analysis, the CGI-C and PGI-C variables will be dichotomized into 2 categories, with “very much improved” and “much improved” into 1 category and the remaining levels in the other category.

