Abbreviations: AE = adverse event, BP = blood pressure, C-SSRS = Columbia Suicide Severity Rating Scale, DFSS = Drooling Frequency and Severity Scale, HIPAA = Health Insurance Portability and Accountability Act, RR = respiration rate, Temp = temperature, USFR = unstimulated salivary flow rate, VAS = visual analog scale, wks = weeks

- (a) All screening and baseline assessments and results must be available before injection of MYOBLOC.
- (b) Telephone follow-up.
- (c) Office visit.
- (d) Office visit. Serves as last visit of current treatment session and first visit of subsequent treatment session. Study drug injection will occur after the 13-week assessments have been completed for the prior treatment session.
- (e) Must be obtained before conducting any study procedure.
- (f) Includes baseline history of aspiration, aspiration pneumonia, choking, and dysphagia.
- (g) Includes 4 bite-wing radiographs or panoramic imaging (if edentulous or if bite-wing x-rays are difficult due to limited teeth). If the subject has no teeth, then the dentist will determine if panoramic imaging is required at any visit after screening.
- (h) Females of childbearing potential only.
- (i) Forced vital capacity will be measured in all subjects with amyotrophic lateral sclerosis and in other subjects if warranted at the discretion of the Investigator.
- (j) When possible, assessments should be done by the same person in a given subject to ensure consistency throughout the study.
- (k) Global measure of effectiveness must be completed before USFR.
- (l) Subject-rated via entry in diary (not during study visit), daily for first 2 weeks after study drug injection and then weekly for remainder of treatment session.
- (m) Subjects will receive injections guided by external anatomical landmarks or by external anatomical landmarks with ultrasound-guided confirmation. Sites designated as "ultrasound" sites will perform all their injections with ultrasound-guidance.
- (n) Subjects will be injected after completion of all assessments and then will be contacted by telephone 24 hours (± 1 day) post-injection to inquire about their health status and remind the subject to complete their diary.
- (o) Telephone follow-up by the study staff will be conducted 1 week (± 1 day) after study drug injection to assess how the subject feels, document adverse events as appropriate, document any new medications the subject may be taking, and remind the subject to complete their diary.

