2.9.1 Effectiveness analysis

As subjects receive multiple single-dose injections, each single-dose injection plus its follow-up period will be considered as a treatment session.

Effectiveness measures obtained over each of the treatment sessions include USFR, CGI-S, CGI-C, DFSS-I, DFSS-S, PGI-S, PGI-C, and DIS at the injection visit (i.e., Day 1, except for CGI-C and PGI-C, and Weeks 13, 26, and 39), 4 weeks post-injection (i.e., Weeks 4, 17, 30, and 43), 8 weeks post-injection (i.e., Week 8, first treatment session only), and 13 weeks post-injection (i.e., Weeks 13, 26, 39, and 52). The injection visit of Day 1 and Weeks 13, 26, and 39 is considered the baseline (or pre-injection), respectively, for each of the consecutive treatment sessions 1 through 4.

For each treatment session, effectiveness analysis of the treatment response will be performed on USFR change from pre-injection, DFSS-I change from pre-injection, and DFSS-S change from pre-injection, CGI-S, CGI-C, PGI-S, PGI-C, and DIS change from pre-injection, at each of the post-injection time points using a t-test.

In addition, the proportion of treatment responders will be reported for the CGI-C and PGI-C at both pre-injection and post-injection time points over each treatment session. Before the analysis, the CGI-C and PGI-C will be dichotomized into 2 categories, with "very much improved" and "much improved" into 1 category and the remaining levels in the other category.

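### A missing pre-injection effectiveness value is filled with the site mean, while the same Week 13/26/39 record stays missing as a post-injection value; the t-test's standard error is then slightly too small

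*SAP*

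**What the plan says.** SAP 2.8 sets two rules for effectiveness data. For outcomes after injection: "Missing post-injection measurements will not be imputed". A missing value before injection, by contrast, "will be imputed by the site-specific average of those subjects who receive the treatment at the corresponding treatment session". Protocol 17.9 has the same pair of rules: "missing measurements at the pre-injection of each treatment session will be imputed by the site-specific average".

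The two rules meet in one record. The schedule footnote for the Week 13, 26 and 39 visits (SAP 2.3) says that such a visit "Serves as last visit of current treatment session and first visit of subsequent treatment session". SAP 2.9.1 accordingly lists Weeks 13, 26 and 39 both as the baselines of sessions 2 to 4 and as the 13-week outcomes of sessions 1 to 3. It tests change from pre-injection with a t-test and makes no allowance for imputed values.

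SAP 2.9.1 and 4.4 also tabulate CGI-C and PGI-C, and their responder proportions, at the pre-injection visits other than Day 1. SAP 2.6.1 makes the corresponding severity score the session baseline for these two scales. The imputation rule does not mention them.

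SAP 2.8 closes, under its heading on repeated records, with: "Any resultant incomplete or missing data of either efficacy or safety parameters will be treated as missing in the statistical analyses involving these parameters".

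**The concern.** Three things follow from the text.

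- **One record, two treatments.** A Week 13 value that was not obtained is absent from the session 1 table and present, as a site mean, in the session 2 table. The n and the mean for the same visit can then disagree within one report.
- **Precision is overstated.** The filled value says nothing about that subject, but the t-test counts it as an observation. Standard errors, 95% intervals and p-values for change from pre-injection are then too optimistic.
- **Category scales.** If the rule is applied to pre-injection CGI-C or PGI-C, it yields fractional scores, and SAP 2.9.1 defines the responder split only by named levels.

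At stake is the accuracy of the effectiveness tables, which serve the secondary objective. The primary safety analysis is not touched: SAP 2.8 leaves missing safety values missing, apart from adverse event start dates.

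**Working it through.** The plan states no standard error, SD, correlation or missing rate, so there is no figure of its own to reproduce.

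**Inputs from the documents.** N = 187 (SAP 2.5); 20 or more sites (protocol synopsis), so about 187/20 = 9 subjects per site; t-test on change (SAP 2.9.1); 5% level and two-sided 95% intervals (SAP 2.9).

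**Assumptions.** Share missing m = 2% to 20%; pre/post correlation rho = 0.2 to 0.8; equal variances; values missing completely at random unless stated.

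**Closed form, one site, in units of sigma²/N.** The estimate is the mean of all post values minus the mean of the observed pre values.

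- True variance: 1 + 1/(1-m) - 2·rho.
- Variance the t-test reports: (1-m)·2(1-rho) + m. Observed pairs contribute 2(1-rho); filled pairs contribute 1.
- The reported variance expands to 2 - m - 2·rho·(1-m). The true variance multiplied by (1-m) gives the same expression. The ratio is therefore exactly 1-m, and reported SE / true SE = sqrt(1-m) whatever rho is.

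Example, m = 10%, rho = 0.5: reported 0.9×1 + 0.1 = 1.000; true 1 + 1.111 - 1 = 1.111; sqrt(1.000/1.111) = 0.949.

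**Multi-site simulation.** N = 187, 20 sites, site-effect SD 0.5 of the within-site SD, 4,000 runs per setting; ranges are over rho = 0.2, 0.5 and 0.8.

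| m | sqrt(1-m) | Simulated SE ratio | Type I error |
|---|---|---|---|
| 2% | 0.990 | 0.986-0.993 | 5.0-5.5% |
| 5% | 0.975 | 0.953-0.965 | 5.6-5.9% |
| 10% | 0.949 | 0.939-0.963 | 5.8-6.3% |
| 20% | 0.894 | 0.898-0.908 | 7.1-7.9% |

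With 40 sites and rho = 0.5 the SE ratio is 0.979 at 5% and 0.887 at 20%. With observed pairs only it is 0.98 to 1.03, with type I error 4.3% to 5.7%: nominal within simulation error.

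**What too small means.** The comparison is with the true sampling error of the same estimate, not with the complete-case SE. At m = 20%, rho = 0.8: reported variance 0.8×0.4 + 0.2 = 0.52, complete-case 0.4/0.8 = 0.50, true 1 + 1.25 - 1.6 = 0.65. The reported SE is 2% above the complete-case SE, but the true SE is 14% above it.

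**Bias.** N = 187, 20 sites, ICC 0.1, rho = 0.6, missingness log-odds 1 per SD of the driver, base rate 10% (about 13% actually missing).

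| Missingness follows | Site-mean filling | Observed pairs |
|---|---|---|
| Pre-injection value | 0.11 SD | 0.05 SD |
| Change score | 0.05 SD | 0.10 SD |

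The order reverses with the driver. In the first row higher pre-injection values go missing, and both methods understate improvement.

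**CGI-C/PGI-C.** For an assumed 7-level distribution with 20% responders, the mean of 8 or 9 ratings is not an integer 88% to 90% of the time. It lies strictly between levels 2 and 3, where the responder split is undefined, 11% to 12% of the time. It is 2 or lower in under 0.1%, so a filled subject would almost never count as a responder.

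**The case against.** The strongest reply is that the rule will seldom fire. The schedule footnotes in SAP 2.3 require baseline results before the first injection, and the 13-week assessments before re-injection. A subject who drops out is not re-injected, so dropout creates no baseline to fill. What remains is an isolated missed item in a treated subject. This stands for clinic measures, and it makes 10% or 20% missing look unlikely there.

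It does not cover DFSS-S, which is entered in a diary outside the visit (SAP 2.3, Table A footnote l). The SAP does not say which diary entry is the pre-injection value. Protocol 14.3.1 has only a practice entry at the Day 1 visit, with the first real entry that evening. A reader might infer that every Day 1 DFSS-S baseline is missing. The documents do not support that: protocol section 10 lists the subject's DFSS among the assessments made before the first injection.

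Three other stronger readings are tempting.

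- **Site-mean filling biases results more than observed pairs.** Not in general: the order reverses when missingness follows the change score.
- **The SAP prescribes invalid CGI-C and PGI-C values.** SAP 2.6.1 makes the severity score their baseline, and a Week 13 CGI-C rates change since the previous injection, so it can be read as a post-injection value that is never imputed. Yet SAP 2.9.1 and 4.4 label the same score pre-injection and the rule has no exemption. The text is ambiguous, and invalid values follow only on the literal reading.
- **The rule breaks down where a site has no observed value in a session.** This is a missing detail. The closing sentence of SAP 2.8 could serve as the fallback, although its position under repeated records leaves that unclear.

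**Conclusion.** The point holds, as a minor one. The inconsistent treatment of the Week 13, 26 and 39 record follows directly from the text and needs no assumption. The standard error is below the true sampling error by a factor of about sqrt(1-m) at any correlation. That result rests on values missing completely at random and on assumed missing rates.

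For clinic measures, a rate of a few percent, and hence an error of a few percent, is the plausible range. DFSS-S could be worse, by an amount the documents do not allow one to state. No direction of bias relative to observed pairs can be claimed. A reader might infer that the effectiveness conclusions are unsafe. The documents do not support that: this is a single-arm safety study with effectiveness as a secondary objective, and the sample size is not built on any efficacy test.

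**What to change.** In SAP 2.8:

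1. Delete the site-mean imputation and analyse change in subjects with an observed pre-injection value.
2. Treat the Week 13, 26 and 39 record identically in both roles.
3. State that CGI-C and PGI-C are never imputed.
4. Report the number missing per visit for each measure.
5. Record this as a change from protocol 17.9, which has the same rule.

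A supportive repeated-measures model on all observed visits is optional. It keeps subjects with a missing baseline only if the pre-injection value is modelled as a response; entered as a covariate, it drops them.

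The cost is a few lines of SAP text and slightly fewer pairs. If gaps are rare, almost nothing is lost; if they are not, the reported intervals need the correction. Observed pairs restore nominal error rates only when values are missing completely at random, so the missing counts in item 4 should be read alongside the results.
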